##### **6.5.4.1 Hematology**

Hemoglobin, hematocrit, red blood cell count, white blood cell (WBC) count with differential (neutrophils including bands, lymphocytes, monocytes, eosinophils, basophils) and platelet count will be measured at all scheduled study visits, within the visit window suggested in [Table 6-1](#).

##### **6.5.4.2 Clinical chemistry**

Serum chemistry will include urea, creatinine, total bilirubin, AST (SGOT), ALT (SGPT), Gamma-Glutamyl Transferase (GGT), alkaline phosphatase, sodium, potassium, bicarbonate, calcium, phosphorous, total protein, albumin, amylase, lipase and uric acid. Serum chemistry will be measured at all scheduled study visits within the visit window specified in [Table 6-1](#).

##### **6.5.4.3 Fasting Laboratory evaluations**

Fasting (8 hour duration with water *ad libitum*) laboratory evaluations will be assessed as at baseline as indicated in [Table 6-1](#).

###### **6.5.4.3.1 Plasma glucose**

Fasting plasma glucose will be taken as a fasting blood sample as indicated in [Table 6-1](#).

###### **6.5.4.3.2 Lipid panel**

A lipid profile including High Density Lipoprotein (HDL), Low Density Lipoprotein (LDL), cholesterol, triglycerides, lipoprotein (a), apolipoprotein B, apolipoprotein A-1, and adiponectin will be measured from a fasting blood sample as indicated in [Table 6-1](#).

#### **6.5.4.4 Urinalysis**

Dipsticks will be provided to the study sites for local urinalysis assessments. The sites will record the results in the appropriate CRF for each subject. Standard dipstick measurements for specific gravity, protein, glucose, pH, blood, urine blood dipstick (non-hemolyzed), urine blood dipstick (hemolyzed), bilirubin, ketones and WBC will be done as indicated in [Table 6-1](#).

#### **6.5.5 Electrocardiogram (ECG)**

A standard single 12-lead ECG will be ECGs will be measured according to the assessment schedule in [Table 6-1](#) and analyzed centrally.

Each ECG tracing should be labeled with study number, subject number, date and time, and filed in the study site source documents. ECGs with subject safety concerns, two additional ECGs should be performed to confirm the safety finding. Clinically significant ECG findings at screening must be discussed with the sponsor before administration with investigational treatment.

[figure not shown]
Although there is no exclusion criterion based on ECG results, the ECG at the screening visit must be reviewed for major abnormalities prior to dosing.

[figure not shown]
[figure not shown]
[figure not shown]
Clinically significant abnormalities should be recorded on the relevant section of the CRF capturing medical history/ Current medical conditions/AE as appropriate.

[figure not shown]
#### **6.5.6 Pregnancy and assessments of fertility**

[figure not shown]
Pregnancy tests will be performed in all women of child-bearing potential (see [Section 4.2](#) for definition of child-bearing potential), as indicated in [Table 6-1](#). Additional pregnancy testing might be performed if requested by local requirements.

Any woman with a confirmed positive pregnancy test during screening is not eligible for randomization. A positive urine pregnancy test during the treatment periods of the study requires immediate interruption of study treatment until a serum  $\beta$ -subunit of human chorionic gonadotropin ( $\beta$ -hCG) is performed and found to be negative. If the serum  $\beta$ -hCG test is positive, the subject must be discontinued from the study treatment.

## **7 Safety monitoring**

### **7.1 Adverse events**

An adverse event (AE) is any untoward medical occurrence (e.g., any unfavorable and unintended sign [including abnormal laboratory findings], symptom or disease) in a subject or clinical investigation subject after providing written informed consent for participation in the

study until the end of study visit. Therefore, an AE may or may not be temporally or causally associated with the use of a medicinal (investigational) product.

In addition, all reports of intentional misuse and abuse of the product are also considered an adverse event irrespective if a clinical event has occurred.

The occurrence of adverse events must be sought by non-directive questioning of the subject at each visit during the study. Adverse events also may be detected when they are volunteered by the subject during or between visits or through physical examination findings, laboratory test findings, or other assessments.

Abnormal laboratory values or test results constitute adverse events only if they fulfill at least one of the following criteria:

- they induce clinical signs or symptoms,
- they are considered clinically significant,
- they require therapy.

Clinically significant abnormal laboratory values or test results must be identified through a review of values outside of normal ranges/clinically notable ranges, significant changes from baseline or the previous visit, or values which are considered to be non-typical in subject with underlying disease. Investigators have the responsibility for managing the safety of individual subject and identifying adverse events. Alert ranges for laboratory and other test abnormalities are included in [Appendix 1](#).

Adverse events must be recorded in the appropriate CRF capturing Adverse Events under the signs, symptoms or diagnosis associated with them, accompanied by the following information:

- the severity grade
  - mild: usually transient in nature and generally not interfering with normal activities
  - moderate: sufficiently discomforting to interfere with normal activities
  - severe: prevents normal activities
- its relationship to the study treatment (suspected: Yes / No)
- its duration (start and end dates) or if the event is ongoing an outcome of not recovered/not resolved must be reported.
- whether it constitutes a serious adverse event (SAE - See [Section 7.2](#) for definition of SAE) and which seriousness criteria have been met.
- action taken regarding study treatment

All adverse events must be treated appropriately. Treatment may include one or more of the following:

- no action taken (e.g. further observation only)
- study treatment dosage increased/reduced
- study treatment interrupted/withdrawn
- concomitant medication or non-drug therapy given
- subject hospitalized/subject's hospitalization prolonged (see [Section 7.2](#) for definition of SAE)

- its outcome (not recovered/not resolved; recovered/resolved; recovered/resolved with sequelae; fatal; or unknown)

Once an adverse event is detected, it must be followed until its resolution or until it is judged to be permanent, and assessment must be made at each visit (or more frequently, if necessary) of any changes in severity, the suspected relationship to the study drug, the interventions required to treat it, and the outcome.

Worsening of psoriasis in this study is evaluated via the use of PASI, IGA mod 2011 and [REDACTED] is not expected to be captured as an AE in the CRF capturing adverse events. Exceptions include cases when a) a new type of psoriasis is diagnosed e.g. guttate psoriasis or b) the worsening of psoriasis is so severe that a qualitatively different status is reached.

Information about common side effects already known about the investigational drug can be found in the Investigator Brochure (IB). This information will be included in the subject informed consent and should be discussed with the subject during the study as needed. Any new information regarding the safety profile of the medicinal product that is identified between IB updates will be communicated as appropriate, for example, via an Investigator Notification or an Aggregate Safety Finding. New information might require an update to the informed consent and has then to be discussed with the subject.

The investigator must also instruct each subject to report any new adverse event (beyond the protocol observation period) that the subject, or the subject's personal physician, believes might reasonably be related to study treatment. This information must be recorded in the investigator's source documents; however, if the AE meets the criteria of an SAE, it must be reported to Novartis.

## **7.2 Serious adverse events**

### **7.2.1 Definition of SAE**

An SAE is defined as any adverse event [appearance of (or worsening of any pre-existing)] undesirable sign(s), symptom(s) or medical condition(s) which meets any one of the following criteria:

- is fatal or life-threatening
- results in persistent or significant disability/incapacity
- constitutes a congenital anomaly/birth defect
- requires inpatient hospitalization or prolongation of existing hospitalization, unless hospitalization is for:
  - routine treatment or monitoring of the studied indication, not associated with any deterioration in condition (specify what this includes)
  - elective or pre-planned treatment for a pre-existing condition that is unrelated to the indication under study and has not worsened since signing the informed consent
  - treatment on an emergency outpatient basis for an event not fulfilling any of the definitions of a SAE given above and not resulting in hospital admission

- social reasons and respite care in the absence of any deterioration in the subject's general condition
- is medically significant, e.g. defined as an event that jeopardizes the subject or may require medical or surgical intervention.

All malignant neoplasms will be assessed as serious under "medically significant" if other seriousness criteria are not met.

Life-threatening in the context of a SAE refers to a reaction in which the subject was at risk of death at the time of the reaction; it does not refer to a reaction that hypothetically might have caused death if it were more severe (please refer to Annex IV, ICH-E2D Guideline).

Medical and scientific judgment should be exercised in deciding whether other situations should be considered serious reactions, such as important medical events that might not be immediately life threatening or result in death or hospitalization but might jeopardize the subject or might require intervention to prevent one of the other outcomes listed above. Examples of such events are intensive treatment in an emergency room or at home for allergic bronchospasm, blood dyscrasias or convulsions that do not result in hospitalization or development of dependency or abuse (please refer to Annex IV, ICH-E2D Guideline).

Any suspected transmission via a medicinal product of an infectious agent is also considered a serious adverse reaction.

### **7.2.2 SAE reporting**

To ensure subject safety, every SAE, regardless of causality, occurring after the subject has provided informed consent and until 12 weeks following the last administration of study treatment must be reported to Novartis safety within 24 hours of learning of its occurrence. Any SAEs experienced after 12 week period following the last administration of study treatment should only be reported to Novartis safety if the investigator suspects a causal relationship to study treatment.

All SAEs reported up to the subject's last visit will be reported in the appropriate eCRF. SAEs beyond the last visit will only be recorded in the Novartis Drug Safety and Epidemiology database.

All follow-up information for the SAE including information on complications, progression of the initial SAE and recurrent episodes must be reported as follow-up to the original episode within 24 hours of the investigator receiving the follow-up information. An SAE occurring at a different time interval or otherwise considered completely unrelated to a previously reported one must be reported separately as a new event.

Information about all SAEs is collected and recorded on the Serious Adverse Event Report Form; all applicable sections of the form must be completed in order to provide a clinically thorough report. The investigator must assess the relationship of each SAE to study treatment, complete the SAE Report Form in English, and submit the completed form within 24 hours to Novartis. Detailed instructions regarding the submission process and requirements for signature are to be found in the investigator folder provided to each site.

Follow-up information is submitted as instructed in the investigator folder. Each re-occurrence, complication, or progression of the original event must be reported as a follow-up to that event regardless of when it occurs. The follow-up information should describe whether the event has resolved or continues, if and how it was treated, whether the blind was broken or not, and whether the subject continued or withdrew from study participation.

If the SAE is not previously documented in the Investigator's Brochure or Package Insert (new occurrence) and is thought to be related to the study treatment a Drug Safety and Epidemiology Department associate may urgently require further information from the investigator for health authority reporting. Novartis may need to issue an Investigator Notification (IN) to inform all investigators involved in any study with the same study treatment that this SAE has been reported. Suspected Unexpected Serious Adverse Reactions (SUSARs) will be collected and reported to the competent authorities and relevant ethics committees in accordance with EU Guidance 2011/C 172/01 or as per national regulatory requirements in participating countries.

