## Post treatment follow-up period

All subjects should enter the post treatment follow-up period, which includes the F4 and F8 follow-up visits. No study treatment (secukinumab) is administered during this period. Follow-up visit F4 is approximately 4 weeks after the EOT 1/EOT 2 visit and 8 weeks after last study treatment administration. Follow-up visit F8 is approximately 8 weeks after the EOT 1/EOT 2 visit, and 12 weeks after the last study treatment administration.

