Subjects who discontinue study treatment before completing the study, and those who prematurely withdraw from the study for any reason should be scheduled for a study visit 4 weeks after their last study treatment administration, at which time all the assessments listed for EOT 1 (Week 16)/EOT 2 (Week 52) will be performed. Then, subjects should return to the study site for further assessments as indicated under the follow-up visits (F4 and F8).

If a subject refuses to return for these assessments or are unable to do so, every effort should be made to contact them or a knowledgeable informant by telephone or by sending appropriate correspondence (i.e. certified letter) immediately. At this contact, the safety (e.g., potential occurrence of AE or SAE) and the primary reason for a subject's premature withdrawal should be determined.

At a minimum, subjects who pre-maturely discontinue the treatment will be contacted for safety evaluations during the 12 weeks following the last dose of study treatment, including final contact at the 12 week point. Documentation of attempts to contact the subject should be recorded in the subject record.

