#### Adverse events

Treatment-emergent adverse events will be summarized. Only primary paths within MedDRA will be considered for adverse event reporting. The definition for “treatment-emergent” is as follows:

- Events started after the first dose of study medication or events present prior to the first dose of study medication but increased in severity based on preferred term
- Started prior to the last dose plus 84 days (inclusive)

AEs will be summarized by presenting, for each treatment group, the number and percentage of subjects having at least one AE, having an AE in each primary system organ class and having each individual AE (preferred term).

Summaries will also be presented for AEs by severity and for study treatment related AEs. If a particular AE ‘severity’ is missing, this variable will be listed as missing and treated as missing in summaries. If a subject reported more than one adverse event with the same preferred term, the adverse event with the greatest severity will be presented. If a subject reported more than one adverse event within the same primary system organ class, the subject will be counted only once with the greatest severity at the system organ class level, where applicable.

Confidence intervals for relative frequencies will be derived as well according to the score method including continuity correction by Newcombe ([Newcombe 1998](#)).

Separate summaries will be provided for death, serious adverse event, other significant adverse events leading to discontinuation and adverse events leading to dose adjustment (including study treatment discontinuation).

Exposure adjusted incidence rates will be provided for selected adverse events.

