2.8.1 Adverse events (AEs)

For adverse events and other binary safety variables crude incidence will be derived as described below.

All adverse events are summarized based on treatment emergent only. The definition for “treatment emergent” is as below:

- events started after the first dose of study medication or events present prior to the first dose of study medication but increased in severity based on preferred term
- and started prior to the last dose plus 84 days (inclusive)

All adverse events will be listed with “treatment emergent” flag displayed.

The crude incidence of treatment emergent adverse events will be summarized by primary System Organ Class (SOC) and Preferred Term (PT). Confidence intervals for the crude rate will be derived using the score method including continuity correction ([Newcombe 1998](#)) as described in [Section 5.4.2.1](#).

Adverse events will be summarized by presenting, for each treatment group, the number and percentage of subjects having at least one AE, having an AE in each primary system organ class and having each individual AE (preferred term). Summaries will also be presented for AEs by severity and for study treatment related AEs. If a particular AE ‘severity’ is missing, this variable will be listed as missing and treated as missing in summaries. If a subject reported more than one adverse event with the same preferred term, the adverse event with the greatest severity will be presented. If a subject reported more than one adverse event within the same primary system organ class, the subject will be counted only once with the greatest severity at the system organ class level, where applicable.

Adverse events will also be summarized by standardized or customized MedDRA queries (SMQ or CMQ/NMQ). The MedDRA version used for reporting the adverse events will be described in a footnote.

The most common adverse events reported ($\geq z$ % in any group for each preferred term in the table by SOC and PT or $\geq z$ % in any group for each grouping term table) will be presented in descending frequency according to its incidence in secukinumab group starting from the most common event. Here threshold value z is set to 2 (%) but it may be updated following review of the dry run outputs.

Separate summaries will be provided for deaths, serious adverse events, other significant adverse events leading to discontinuation and adverse events leading to dose adjustment or interruption.

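### SAE entry in the eCRF stops at the subject's last visit, while the treatment-emergent window runs to last dose + 84 days; the two limits differ for subjects who stop attending early

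*Protocol*

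**What the plan says.** Protocol 7.2.2 sets two limits for SAEs. Reporting to the sponsor's safety group starts at consent, applies whatever the causality, and continues: "until 12 weeks following the last administration of study treatment must be reported to Novartis safety within 24 hours". Entry in the study database has a different limit: "All SAEs reported up to the subject's last visit will be reported in the appropriate eCRF". After that, "SAEs beyond the last visit will only be recorded in the Novartis Drug Safety and Epidemiology database".

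The analysis window follows the first limit. Under SAP 2.8.1 an event that began or worsened after the first dose is treatment-emergent if it also meets the second condition, "and started prior to the last dose plus 84 days (inclusive". Protocol 9.5.2 uses the same 84 days. Neither text shortens the window for a subject whose visits end sooner. For the tables, SAP 2.8.1 states: "Separate summaries will be provided for deaths, serious adverse events, other significant adverse events leading to discontinuation". SAP 2.8.3 adds a summary and listing of deaths.

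The planned final visit is placed at the end of this window: "Follow-up visit F8 is approximately 8 weeks after the EOT 1/EOT 2 visit, and 12 weeks after the last study treatment administration" (Protocol 3.1). Subjects who stop treatment early are, as a minimum, to be "contacted for safety evaluations during the 12 weeks following the last dose of study treatment, including final contact at the 12 week point" (Protocol Section 6).

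**The concern.** The protocol asks sites to look for SAEs after a subject has stopped attending, then directs what they find away from the eCRF. Protocol 8.3 describes the database that is locked for analysis and mentions laboratory, ECG and IRT data coming in. It mentions no transfer from, or reconciliation with, the safety database. SAP 2.8.1 and 2.8.3 name no data source for the SAE and death tables.

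SAP 5.4.2.2 estimates crude incidence as x/n. A subject whose SAE is learned of by telephone 70 days after the last dose, after the final visit, would then stay in n and add nothing to x, although the event lies inside the plan's own window.

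At stake is the completeness of the SAE tables in a study meant to evaluate the safety of higher exposure (Protocol 3.2). Some special-interest categories in SAP Table 2-6 may hold few events, so one omission could show. The study report could also disagree with the safety database on SAEs for the same stated window.

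**Working it through.** **Step 1: reproduce the schedule.** Day = 7 × week + 1. The last planned dose is at Week 48 (Protocol 3.1): 7 × 48 + 1 = Day 337. The window ends at 337 + 84 = Day 421. F8 is Day 421 in Protocol Table 6-1 and SAP Table 2-1. The match is exact, so a subject who attends F8 on schedule has no gap.

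**Step 2: size of the gap otherwise.** Gap = (last dose + 84 days) − last attended visit.

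| Last attended visit | Days after last dose | Gap (days) |
|---|---|---|
| F8, on schedule | 84 | 0 |
| F4 | 56 | 28 |
| EOT | 28 | 56 |
| Last dosing visit | 0 | 84 |

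Home dosing can widen this. The Week 40 site visit is Day 281, and Protocol 5.5.4 allows home doses to Week 48. A subject who doses at home to Week 48 and never returns has 421 − 281 = 140 days. This is an extreme case.

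**Step 3: expected number of SAEs in the gap.** Expected SAEs = subjects × (gap / 365.25) × SAE rate per subject-year. The documents give no dropout rate and no SAE rate for this trial, so these are assumptions:
- 5% to 10% of 330 subjects have EOT as their last visit (16.5, taken as 17, to 33);
- the gap is 56 days, and 56/365.25 = 0.1533 years;
- there are 5 to 15 SAEs per 100 subject-years.

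Results:
- 17 × 0.1533 × 0.05 = 0.13
- 26 × 0.1533 × 0.08 = 0.32
- 33 × 0.1533 × 0.15 = 0.76

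**Step 4: a wider range.** Protocol 3.6 gives 2.5% and 4.9% for the two arms of a 16-week interval-shortening study. Its wording leaves open whether these are all SAEs or related ones only. Per subject-year:
- 0.025 / (112/365.25) = 0.0815
- 0.049 / (112/365.25) = 0.1598

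With 5% to 15% of subjects not attending and gaps of 28 to 84 days:
- low: 330 × 0.05 × (28/365.25) × 0.0815 = 0.10
- high: 330 × 0.15 × (84/365.25) × 0.1598 = 1.82

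For scale, 330 subjects followed for 421 days give 330 × 421/365.25 = 380.4 subject-years, or about 31 to 61 SAEs at the same rates.

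**The case against.** The strongest reply is that neither document defines the last visit. Subjects who stop treatment stay in the study and should return for EOT, F4 and F8 (Protocol 5.6.2). Nobody is lost to follow-up until the scheduled end-of-study visit has passed (5.6.4). Completion means the last planned visit (5.6.1), and AE collection runs to the end-of-study visit (7.1). Read this way, 7.2.2 only separates in-study from post-study SAEs, and both limits fall on Day 421. The ambiguity is real. But 7.2.2 speaks of the individual subject's visit, Section 6 treats contacts as distinct from visits, and SAP 2.4.1 provides for last visits before day 84 and ends exposure there. If the 12-week contact was meant to count as a visit, the gap closes for contacted subjects, and the protocol should say so.

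Stronger readings are tempting, but the documents do not support them:
- **A reader might infer that the tables are shown to omit these events.** That the tables draw on eCRF data alone is an inference from 7.2.2 and from the silence of Protocol 8.3 and SAP 2.8. A reconciliation may exist unwritten.
- **A reader might infer a biased comparison of regimens, on the view that non-attenders are the likeliest to have serious events.** Nothing in the documents shows a difference between arms or a raised risk after attendance stops. SAEs reported by the EOT visit, including those that led to stopping, are already in the eCRF. After consent is withdrawn, contact is largely barred (Protocol 5.6.3).
- **A reader might infer that deaths are lost.** Survival status is collected at follow-up (5.6.1) and the reason for discontinuation goes on the disposition CRF (5.6.2), so a death may reach the study database by another route.
- **A reader might infer that safety oversight fails.** It does not: every SAE within 12 weeks must still reach the sponsor within 24 hours of being learned of.
- **A reader might extend the point to completers whose F8 is early.** The SAP window for F8 opens at Day 408, which leaves at most 421 − 408 = 13 days, and the 12-week contact is required only of subjects who stopped early. This is negligible.

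One objection concerns the remedy and stands. SAP 2.1.5 and 2.4.1 end exposure at the earlier of the last visit and last dose + 84 days. Adding later SAEs without moving that limit would put events in the numerator with no matching time in the denominator, and Protocol 9.5.2 plans exposure-adjusted rates for selected AEs.

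**Conclusion.** The point holds as a minor inconsistency. On its natural reading, 7.2.2 keeps out of the eCRF some SAEs that the plan itself calls treatment-emergent. The subjects concerned are those whose last attended visit precedes last dose + 84 days and who are still contacted. Unless an unstated reconciliation exists, these SAEs would be missing from the crude-incidence tables.

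The expected loss is about 0.1 to 0.8 SAEs over both arms, and up to about 1.8 on the wider assumptions. Both ranges rest on assumed dropout. The first also assumes the SAE rate; the second borrows it from another study. The point does not establish bias between the arms, and it is weaker for deaths than for other SAEs.

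**What to change.** - **Protocol 7.2.2:** require eCRF entry of all SAEs, including fatal ones, with onset up to 84 days after the last dose, whatever the date of the last visit. Only later SAEs go solely to the safety database.
- **SAP 2.8.1 and 2.8.3:** state that the SAE and death tables include all such events after reconciliation with the safety database.
- **Exposure-adjusted SAE rates, if produced:** end follow-up at the earlier of last contact and last dose + 84 days, so that numerator and denominator match.

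The cost is a few sentences, an update to the eCRF completion guideline and a few extra entries at sites. No new contact is needed, because Section 6 and 7.2.2 already require these events to be sought and reported. The downside is that after the last visit serious events would be captured and non-serious ones would not. A footnote to the overall AE tables should say so.
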